8.4 Secondary Efficacy Analyses

The point estimate of the responder rate, odds ratio, and corresponding 95% confidence intervals will be derived from a generalized linear mixed model (GLMM) with a logit link function to compare the probability of having responder between treatment groups of each visit of Week 4, Week 8, Week 12, Week 24, Week 36, Week 52. The model will include time from last known normal and initiation of first dose (≤ 12 hours, > 12 hours), tPA use (Y/N), EVT use (Y/N), visit, treatment group as fixed effects, and visit as the random effect by subject. An unstructured variance covariance matrix will be used. The compound symmetry variance covariance matrix will be used if the model does not converge with unstructured matrix.

[figure not shown]

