1 SYNOPSIS

Title: A Randomized, Double-Blind, Placebo-Controlled Proof-of-Concept Study to Assess the Safety and Efficacy of Elezanumab in Acute Ischemic Stroke	
Background and Rationale:	Elezanumab is an investigational product under development for improvement of neurologic function in patients with acute ischemic stroke. Treatment of acute ischemic stroke patients with elezanumab has the potential to accelerate recovery and/or provide more complete recovery by decreasing neuronal damage and enhancing restoration of neuronal activity.
Objectives and Endpoints:	
The objectives are to assess the efficacy, safety, tolerability, and pharmacokinetics (PK) of elezanumab in subjects with acute ischemic stroke.
 
The primary endpoint is the National Institutes of Health Stroke Scale (NIHSS) total score during the Treatment Period.
 
The secondary endpoint is a favorable outcome based on the modified Rankin Scale (mRS) at Week 52. A favorable outcome is defined as having an mRS score of 0, 1, or 2 at the specified time point.

Investigator(s):	Multicenter
Study Site(s):	Approximately 45 sites in multiple countries.
Study Population and Number of Subjects to be Enrolled:	
Adult male or female, 30 to 90 years of age, inclusive, with a clinical diagnosis of acute ischemic stroke in anterior circulation and able to randomize within 24 hours of "last known normal" (the time before hospital arrival at which time the subject was last known to be without the signs and symptoms of the current stroke or at his or her baseline state of health), supported by acute brain computed tomography (CT) or magnetic resonance imaging (MRI).
 
Approximately 120 subjects will be randomized to receive elezanumab 1800 mg or placebo in a 1:1 ratio.

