- ✓ 7. NIHSS total score of 7 to 21, inclusive. NIHSS eligibility must be confirmed within 1 hour before randomization. For subjects treated with IV tPA \pm EVT, NIHSS must be confirmed \geq 1 hour after completion of all treatments and once any confounding effects of sedation or anesthesia have resolved.
- ✓ 8. No evidence of acute seizure at the onset of index stroke based on assessments conducted per standard of care. Subjects with evidence of seizure at onset of index stroke, but with imaging conclusively demonstrating an acute ischemic stroke are still allowed.
- ✓ 9. No evidence of acute myocardial infarction based on assessments per standard of care (e.g., elevated troponin levels, abnormal ECG).
- ✓ 10. In the judgment of the investigator, symptoms are not considered likely to resolve within the subsequent few hours (e.g., transient ischemic attack [TIA]).

Subject History

- ✓ 11. Subjects or their legally authorized representative confirms that before index stroke, there was no substantial impairment in subject's ability to perform activities of daily living (e.g., dressing, eating, walking, bathing, toileting) without assistance, as defined by a modified Rankin Score (mRS) of 0 to 2 before the index stroke.
- ✓ 12. Subjects with a history of previous stroke more than 3 months before enrollment are allowed if they are no longer experiencing ongoing functional recovery and mRS remains 0 to 2 prior to index stroke.
- ✓ 13. No known history before randomization of clinically significant medical conditions (other than current acute ischemic stroke) or any other reason, including any physical, psychological, or psychiatric condition that in the investigator's opinion would compromise the safety or interfere with the subject's participation in this study, or would make the subject an unsuitable candidate to receive study drug, or would put the subject at risk by participating in the study. Subjects with comorbid conditions that are, in the opinion of the investigator, clinically stable and not expected to meaningfully progress in the following 12 months may be considered eligible.
- ✓ 14. No known medical history of repeated episodes of complex migraine (e.g., weakness, vision, difficulty speaking). Subjects with history of complex migraine, but with imaging conclusively demonstrating an acute ischemic stroke are still allowed.

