7.3 Statistical Analyses for Efficacy

General Considerations

Analysis of the primary, secondary, and all other efficacy endpoints will be conducted on the FAS based on treatment as randomized, unless otherwise specified in the SAP.

The primary and secondary endpoints will be assessed using Bayesian methodology. No formal hypothesis tests will be performed. Additional efficacy endpoints will be summarized using descriptive statistics including the number of observations, mean, standard deviation, minimum, median, and maximum for continuous variables, and number and percent for categorical variables.

For continuous exploratory efficacy endpoints, the between-group treatment summary at each visit will be conducted using a mixed effects model with repeated measures (MMRM) including treatment group, visit, treatment-by-visit interaction, and stratification factors as fixed effects, the baseline values associated with the endpoint as covariates unless otherwise noted in the SAP. Missing data will not be imputed before performing the MMRM.

For binary efficacy endpoints, the frequency and percentage will be provided by treatment group. Missing values will be imputed as non-responders unless otherwise specified in the SAP.

Primary Efficacy Analysis

The primary analysis on NIHSS total score during the Treatment Period will be based on the AUC derived from an MMRM. The monthly-adjusted AUC of NIHSS total score for each treatment group will be obtained using the trapezoidal method and will be adjusted for month by dividing by 12. The MMRM model will include covariates of time since last known normal (≤ 12 hours, > 12 hours based on actual time of study drug initiation), IV tPA use, EVT use, main effects of treatment group and visit, and treatment-by-visit interaction. Each visit by a subject will serve as a repeated measure.

The posterior probability of the treatment group difference (with treatment showing greater improvement than placebo) in monthly-adjusted AUCs being greater than 0.6 using a noninformative prior will be calculated.

Secondary Efficacy Analysis

The secondary efficacy analysis is the proportion of subjects with a favorable outcome based on an mRS at Week 52 of 0, 1, or 2. The posterior probability of the treatment group difference (with treatment showing greater improvement than placebo) in responder rates being greater than 6.25% will be calculated using a non-informative prior.

Additional Efficacy Analyses

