3.2 Secondary Endpoint

The secondary endpoint is the proportion of subjects with a favorable outcome based on the modified Rankin Scale (mRS) at Week 52. A favorable outcome is defined as having an mRS score of 0, 1, or 2 at the specified time point.

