8.2 Handling of Missing Data

Missing data will be imputed using the following methods for the efficacy analyses:

- Non-Responder Imputation (NRI): the NRI analysis will categorize any subject who does not have evaluation during a specific visit window as a non-responder for that visit. Unless otherwise noted, this will be the primary approach for accounting for missing data in responder analyses.
- Generalized linear mixed model (GLMM): The model will include a logit link function to compare the probability of having responder between treatment groups of each visit of Day 2-4, Week 4, Week 8, Week 12, Week 24, Week 36, Week 52, and will include baseline NIHSS as a covariate and time from last known normal and initiation of first dose (≤ 12 hours, > 12 hours), tPA use (Y/N), EVT use (Y/N), visit, and treatment group as fixed effects. An unstructured variance covariance matrix will be used. The compound symmetry variance covariance matrix will be used if the model does not converge with unstructured matrix. The GLMM model relies on a missing at random (MAR) assumption.
- As Observed (AO): The AO analysis will not impute values for missing evaluations, and thus a subject who does not have an evaluation on a scheduled visit will be excluded from the AO analysis for that visit. AO will include all values collected in the study.
- MMRM: The repeated measures analysis will be conducted using a mixed model including observed measurements at all visits. The mixed model includes the categorical fixed effects of treatment, visit and treatment-by-visit interaction, main stratification factors at randomization, and the continuous fixed covariates of baseline measurement, unless otherwise noted. An unstructured variance-covariance matrix will be used; if the model does not converge, then a compound symmetry variance-covariance matrix will be used. Denominator degrees of freedom will be computed using the Kenward-Roger method. Parameter estimation is based on the assumption of data being missing at random and using the method of restrictive maximum likelihood. MMRM will be the primary approach in the analysis of continuous

variables unless otherwise noted. The MMRM model relies on a missing at random (MAR) assumption.

For all analyses related to the mRS, if a subject has a value of 6 (dead), this will be carried forward to future visits in the analysis. This will be applied to all mRS analyses, including the responder analysis as observed.

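### The SAP's model for the secondary mRS endpoint omits baseline NIHSS, which its general responder model includes; the two specifications should be reconciled and the covariate added

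*SAP*

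**What the plan says.** The secondary endpoint is the proportion with a favorable mRS at Week 52 (SAP 3.2): "A favorable outcome is defined as having an mRS score of 0, 1, or 2 at the specified time point". SAP 8.4 takes the responder rate and odds ratio from a logit-link generalized linear mixed model (GLMM). Its terms are time from last known normal to first dose, then "tPA use (Y/N), EVT use (Y/N), visit, treatment group as fixed effects, and visit as the random effect by subject". It covers "each visit of Week 4, Week 8, Week 12, Week 24, Week 36, Week 52".

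SAP 8.2, the general section on missing data, also describes a logit-link GLMM for responders. That model "will include baseline NIHSS as a covariate and time from last known normal and initiation of first dose", followed by tPA, EVT, visit and treatment. It covers "each visit of Day 2-4, Week 4, Week 8, Week 12, Week 24, Week 36, Week 52".

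Protocol 7.3 asks, for the same endpoint, for the posterior probability of a treatment difference "in responder rates being greater than 6.25% will be calculated using a non-informative prior". It names no covariates for that calculation. The entry criterion is "NIHSS total score of 7 to 21, inclusive" (protocol 5.1), and the size is given in the synopsis: "Approximately 120 subjects will be randomized to receive elezanumab 1800 mg or placebo in a 1:1 ratio".

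**The concern.** A single SAP gives two covariate sets for a responder GLMM, and the set attached to the secondary endpoint has no term for stroke severity. Protocol 4.2 says that milder strokes may recover substantially without treatment and that the most severe carry more death, disability and early discontinuation. Entry scores span 14 NIHSS points, and randomization is stratified on tPA, EVT and time since last known normal only (protocol 5.8, SAP 2.3). Severity balance between two arms of about 60 is therefore left to chance.

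Two things are at stake. The responder difference moves with whatever imbalance occurs, and some precision is lost. In addition, unreconciled specifications leave a choice of model that could be made after the data are seen.

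**Working it through.** **No figure to reproduce.** The documents give no standard error or power for mRS, and the redacted sample-size inputs concern the NIHSS AUC. The check is therefore a comparison of texts, then a calculation on stated assumptions.

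**1. The two models.**

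| | SAP 8.2 | SAP 8.4 |
|---|---|---|
| Link | logit | logit |
| Time since last known normal, tPA, EVT, visit, treatment | yes | yes |
| Baseline NIHSS | yes | no |
| Random effect stated | no | visit, by subject |
| First visit | Day 2-4 | Week 4 |

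Severity does not enter 8.4 by another route. SAP 8.1 makes baseline one of the repeated timepoints, but for continuous variables, and the 8.4 visits start at Week 4.

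**2. Expected imbalance.** The SD of the between-arm difference in mean NIHSS is SD × √(2/60). The NIHSS SD is not given; 3.5 to 4.3 is assumed (a uniform spread over 7–21 gives 4.32).
- SD 3.5: 3.5 × 0.1826 = 0.64 points; a difference of 1 point or more has probability 12%.
- SD 4.3: 4.3 × 0.1826 = 0.79 points; probability 20%.

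**3. Shift in the responder difference.** The base case was 3,000 simulated trials per scenario, 60 per arm, stratified blocks, and a Week 52 logistic model with assumed slopes of −0.12 to −0.18 per point. A one-SD imbalance of 0.6 points moved the difference by 1.6 to 2.3 percentage points. As a hand check, the shift cannot exceed about slope × 0.25 × imbalance, because p(1−p) is at most 0.25: 0.12 × 0.25 × 0.6 = 1.8 points and 0.18 × 0.25 × 0.6 = 2.7 points. The simulated values lie just below these ceilings, as they should.

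**4. Precision of the risk difference.** In the two base scenarios the mean standard error fell from 0.0890 to 0.0856 (3.8%) and from 0.0895 to 0.0878 (1.9%). As a scale check, 45% against 57% with 60 per arm gives √[(0.2475 + 0.2451)/60] = 0.091 without any adjustment.

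**5. Sensitivity to the slope.** A second simulation used 4,000 trials per scenario, a placebo rate of 45%, no missing data, and NIHSS SD 3.54 or 4.32:

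| Odds ratio per NIHSS point (log) | Shift per one-SD imbalance, points | Variance reduction from adjusting |
|---|---|---|
| 0.90 (−0.105) | 1.7–2.2 | 2–5% |
| 0.85 (−0.163) | 2.3–3.1 | 6–11% |
| 0.80 (−0.223) | 3.1–3.7 | 11–17% |
| 0.75 (−0.288) | 3.8–4.9 | 17–27% |

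With the covariate in the model, the remaining shift was at most 0.3 percentage points per NIHSS point.

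**6. Odds-ratio scale.** In a single-visit logistic model, adding NIHSS raises the standard error of the log-odds ratio (0.37 to 0.38–0.45). The gain appears in a larger estimate and z, for example mean z 1.62 to 1.76 at an odds ratio of 0.80 per point. In a six-visit random-intercept GLMM (250 trials per scenario), adjustment lowered that standard error from 0.62 to 0.55 at a subject-level slope of −0.35, and from 0.62–0.64 to 0.46–0.48 at −0.50. Those are steeper assumptions than the base case, and neither simulation is the exact 8.4 model.

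**7. The 6.25% probability, if it comes from this model.** At an observed difference of 12 points with a standard error of 8.9, it is Φ[(12 − 6.25)/8.9] = Φ(0.646) = 0.74. A 2.3-point shift either way gives Φ(0.388) = 0.65 to Φ(0.904) = 0.82. A 1.6-point shift gives 0.68 to 0.80.

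**The case against.** **The sections may serve different purposes.** SAP 8.2 is a general section and names no endpoint. Its visit list matches the NIHSS change-from-baseline list in SAP 8.3.4, so that GLMM may have been written with another endpoint in mind. A reader might infer that 8.4 removed a covariate that had been specified for mRS. The documents do not support that; they show two unreconciled specifications. The difference still needs an explanation, because 8.2 does not limit its GLMM to other endpoints and 8.4 gives no reason.

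**The threshold may not depend on this model.** No visible SAP text says that the 6.25% probability is computed from the 8.4 GLMM. SAP 8.2 makes non-responder imputation the default for responder analyses, and SAP 8.1 gives a Wald difference. If the probability came from those unadjusted rates, editing the 8.4 covariates alone would not change it, although the unadjusted rates have the same exposure to imbalance. The 0.65 to 0.82 range is therefore conditional. It is also not uncertainty on top of the standard error: (2.3/8.9)² = 6.7% of the sampling variance, already counted in the 8.9.

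**Missing data.** A reader might infer that deaths undermine the missing-at-random assumption here. They do not: SAP 8.2 carries mRS 6 forward, so deaths are observed non-responders. Only dropout remains. Earlier mRS values carry some severity information, and this part was not quantified.

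**Severity is examined elsewhere.** SAP 7.2 summarizes baseline NIHSS by arm, and SAP 8.6 repeats the mRS responder table below and at or above a score of 15. These would reveal an imbalance but would not correct the main estimate. SAP 8.6 also adjusts for baseline NIHSS in its subgroup ANCOVA of NIHSS change, so the sponsor already uses the covariate.

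**Redaction.** Text after 8.4 and 8.4.1 is not shown, so an adjusted sensitivity analysis may exist. The covariate sentence in 8.4 itself reads as complete.

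**Conclusion.** The point holds as an unreconciled specification with a modest, avoidable cost. Randomization keeps the 8.4 analysis valid on average, so a reading of systematic bias would go too far. What remains is dependence on chance severity imbalance (about 1.6 to 2.3 percentage points per one-SD imbalance) and a standard error of the risk difference about 2% to 4% larger than needed. Both are larger if NIHSS predicts mRS more strongly than assumed.

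The sizes rest on figures that the documents do not give: the slope of mRS on NIHSS, the NIHSS SD and the placebo response rate. They come mainly from single-visit models. The study is exploratory, with no type I error control and no p-values, which limits the consequence. The change is still worth making because it costs almost nothing.

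**What to change.** In SAP 8.4, add continuous baseline NIHSS as a fixed covariate. Align 8.2 with 8.4: either make them one model with one visit list, or say which endpoints the 8.2 GLMM serves and why its visits differ. State in 8.4 that the Week 52 responder difference used for the 6.25% posterior probability comes from the adjusted model. When doing so, note that the visible 8.4 terms include no treatment-by-visit interaction, so the SAP should say how the Week 52 difference is obtained.

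The covariate is a one-line change using a variable already collected; the alignment adds a few sentences. A Week 52 risk difference standardized over the covariates of the Full Analysis Set is optional. It takes more work, because it requires integrating over the random effects and choosing a standard-error method.

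### Read literally, the secondary-endpoint GLMM in SAP 8.4 gives subject-specific responder rates and odds ratios that cannot be compared with the protocol's 6.25-point difference; the SAP should state a marginal or standardised analysis

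*SAP*

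**What the plan says.** **Protocol 7.3** sets the secondary analysis on the proportion scale. It asks for the posterior probability of a treatment-group difference "in responder rates being greater than 6.25% will be calculated using a non-informative prior". For binary efficacy endpoints it gives frequency and percentage by arm, with missing values counted as non-responders unless the SAP specifies otherwise.

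**SAP 8.4** describes a different output: "The point estimate of the responder rate, odds ratio, and corresponding 95% confidence intervals will be derived from a generalized linear mixed model", with a logit link. The comparison is "between treatment groups of each visit of Week 4, Week 8, Week 12, Week 24, Week 36, Week 52", which is six visits. The terms are the three stratification factors, then "visit, treatment group as fixed effects, and visit as the random effect by subject". On covariance: "An unstructured variance covariance matrix will be used". The fallback: "The compound symmetry variance covariance matrix will be used if the model does not converge with unstructured matrix". No treatment-by-visit term is listed. The visible text has no rate difference and no step that averages over the random effects.

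**Elsewhere in the SAP.** Section 8.1 gives a default for responder analyses: a difference in proportions with Wald limits, unless otherwise specified. Section 8.2 makes non-responder imputation the primary approach for responder analyses unless otherwise noted. Section 13.1 declares no change from the protocol's planned analyses.

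**The concern.** The protocol's quantity is a difference between two arm proportions at Week 52. In a logit model with random effects, a rate obtained by inverting the link at the fixed effects applies to a subject whose random effect is zero. The odds ratio is likewise conditional on the random effect. Neither equals its population counterpart unless the random-effect variance is zero.

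The random effect described here is also an awkward one. Each subject contributes one binary value per visit, so a random visit effect within subject puts a separate variance on every single observation. Binary data carry no residual scale against which to estimate that variance, so it trades off against the size of the fixed effects. Compound symmetry, if it too is a random visit effect, keeps the same per-visit variance. It is also invoked only on non-convergence, so a fit that converges but says little about the variance would be reported.

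At stake is interpretation. The plan presents no p-values and makes no type I error claim, so readers will rely on the estimates. They could see reported rates that are not the arms' proportions and set their difference against 6.25 points.

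**Working it through.** The documents state no power, rate or operating characteristic for the secondary endpoint, so there is no figure of the plan to reproduce.

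**Inputs from the documents.** Threshold 6.25 points (Protocol 7.3). Six visits, unstructured matrix, logit link (SAP 8.4). About 120 subjects, 1:1 (Protocol synopsis), so 60 per arm.

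**Assumptions, not in the documents.** Placebo responder rate 15% to 50%. Random-effect variance 1 to 9. For step 3, latent within-subject correlation 0.6 or 0.8 and illustrative visit rates that end at 40% vs 46.25%.

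**1. Parameter count.** Covariance: 6 × 7 / 2 = 21. Fixed effects: 1 intercept + 5 visit + 1 treatment + 3 stratification factors = 10. Data: at most 120 × 6 = 720 correlated binary values.

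**2. Scale.** For an arm with population rate p and random-effect SD s, solve for η in p = E[expit(η + sZ)], Z standard normal (80-point Gauss-Hermite quadrature). The rate at random effect zero is expit(η). The conditional odds ratio is exp(η₁ − η₀). The true difference is 6.25 points in every row.

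| True rates | Variance | Rates at random effect zero | Difference (points) | Odds ratio (population value) |
|---|---|---|---|---|
| 15% vs 21.25% | 1 | 11.4% vs 17.3% | 5.9 | 1.63 (1.53) |
| 15% vs 21.25% | 9 | 2.6% vs 5.9% | 3.2 | 2.30 (1.53) |
| 30% vs 36.25% | 1 | 26.5% vs 33.6% | 7.1 | 1.40 (1.33) |
| 30% vs 36.25% | 4 | 20.0% vs 28.3% | 8.3 | 1.58 (1.33) |
| 30% vs 36.25% | 9 | 13.9% vs 22.7% | 8.8 | 1.82 (1.33) |
| 40% vs 46.25% | 4 | 33.9% vs 43.8% | 9.9 | 1.52 (1.29) |
| 50% vs 56.25% | 1 | 50.0% vs 57.5% | 7.5 | 1.36 (1.29) |
| 50% vs 56.25% | 9 | 50.0% vs 63.3% | 13.3 | 1.73 (1.29) |

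The shift goes in both directions, so no constant correction exists. Conversely, at a 40% placebo rate a conditional odds ratio of 1.5 means a population difference of 10.0, 8.3, 6.0 or 4.6 points at variance 0, 1, 4 or 9. It falls on either side of 6.25 depending on the variance.

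**3. Identification.** This check used the simpler compound-symmetry form: a subject variance plus an independent per-visit variance. Population rates were held fixed, the per-visit variance was raised and the subject variance re-optimised. The expected log-likelihood loss over the 2⁶ = 64 response patterns was then computed for 120 subjects.

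| Latent correlation | Total SD | Log-likelihood loss | Week 52 odds ratio | Difference at random effect zero (points) |
|---|---|---|---|---|
| 0.6 | 2.2 | 0 (reference) | 1.57 | 10.5 |
| 0.6 | 3.7 | 0.03 | 1.93 | 14.4 |
| 0.6 | 5.6 | 0.05 | 2.56 | 18.1 |
| 0.8 | 3.6 | 0 (reference) | 1.90 | 14.2 |
| 0.8 | 5.5 | 0.04 | 2.52 | 18.0 |

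A loss of 0.05 units cannot be detected, yet the reported odds ratio moves by a full unit. The unstructured matrix has more freedom still. Population rates were fixed throughout, so they remain estimable; what the data barely determine is the scale.

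**4. The protocol's own quantity.** With 60 per arm, an assumed 40% placebo rate, a flat prior and a normal approximation, SE = √(0.40 × 0.60/60 + 0.4625 × 0.5375/60) = 0.090. With the SE recomputed at each observed rate, observed differences of 6.25, 10 and 15 points give posterior probabilities of 0.50, 0.66 and 0.83. Only the two Week 52 proportions are needed.

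**The case against.** - **A residual-side covariance may be meant.** Unstructured first and compound symmetry on non-convergence is the same sequence that SAP 8.3.3 uses for the residual covariance of the primary model. The general GLMM description in SAP 8.2 uses the same covariance wording and names no random effect. With a marginal covariance the rates and odds ratio would be population-averaged, and the identification problem would largely go. This stands as a possibility. But SAP 8.4 calls visit a random effect, while 8.3.3 names the REPEATED statement, so the visible text does not settle it.
- **The 6.25-point step may be hidden.** A reader might infer that the SAP dropped the protocol's posterior probability. The documents do not support that: a block that is not shown follows the model paragraph in SAP 8.4, and 8.4.1 contains a redacted area. The point is only that the outputs described are not that quantity.
- **A crude difference is probably planned anyway.** SAP 8.1 and 8.2 give a Wald difference with non-responder imputation by default, and SAP 8.6 repeats the mRS 0-2 responders by subgroup on that basis. The protocol does not tie the posterior probability to a GLMM. This stands, and it means that nobody has been shown to intend setting GLMM output against 6.25 points. It also means that two Week 52 rates per arm, on different scales, could appear side by side.
- **The size is assumed.** At variance 1 the shift is about one point or less. No base rate or variance comes from the documents.
- **The study is exploratory.** There are no formal tests, and no visible action depends on the 6.25-point probability. A conditional odds ratio is a legitimate summary if labelled as such. Both are true, and they limit the harm to interpretation.

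**Conclusion.** The concern holds for the model as literally written. Its inverse-link rates and odds ratio are subject-specific and rest on a weakly identified variance. They are not the arms' Week 52 proportions, and their difference cannot be set against 6.25 points.

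Under the assumed rates and variances a true 6.25-point difference would read as about 3 to 13 points, and as 5.9 to 7.5 at variance 1. This assumes that visit is fitted as a subject-level random effect and that rates come from the inverse link with no averaging. If a marginal covariance is intended, most of the problem disappears and what remains is a need to say so.

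Separately, with no treatment-by-visit term in the listed model, its odds ratio is one common effect across six visits and not a Week 52 effect.

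A reader might go further and conclude that the secondary result will be wrong by a known amount, or that error rates are affected. Neither follows. The size depends on quantities that the documents do not give, and no type I error claim is made.

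**What to change.** In SAP 8.4:

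1. State which covariance is meant. Use either a marginal model (residual-side or GEE), or a subject random intercept with rates integrated over the intercept and averaged over the covariates.
2. Add treatment-by-visit, so that Week 52 has its own effect.
3. Report population-averaged Week 52 rates and their difference, with a delta-method or bootstrap interval. Label any conditional odds ratio as conditional.
4. Compute the posterior probability of a difference above 6.25 points from the Week 52 proportions with the protocol's non-responder imputation. If a redacted block already does this, cross-refer to it.
5. Present the standardised model-based difference as a sensitivity analysis under MAR. Unweighted GEE needs a stronger assumption than MAR, so the random-intercept route suits this role better.

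Cost: SAP wording and a short programming step, with no new data. The interaction term will widen the Week 52 interval slightly. A random intercept assumes equal latent correlation between all visits, which should be stated.
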